5.11.4 Recording YSI Results

The YSI source documents will be labeled as follows throughout the study to facilitate matching glucose results.

Sample identification will include:

- 1) Ascensia serum traceability control level or
- 2) Subject ID plus either 'capillary' or 'venous' blood

The YSI source documents (tapes) will be affixed to plain white paper and photocopied to preserve the image on the thermal paper, and will be stored in individual subject's study file for source data verification.

NOTE: If glucose results are not to be used due to operator errors, insufficient sample, etc., this should be clearly marked on the YSI source document.

The YSI operator will record all non-numeric codes - QNS (Quantity not sufficient), NO (Not Obtainable), and error codes as appropriate for the YSI tests.

5.12 Subject Questionnaires

Site staff will administer two questionnaires to subjects. Questionnaire 1 will be given to all subjects and Questionnaire 2 will be given only to subjects with diabetes.

5.12.1 Questionnaire 1: Evaluation of Instructions for Use. (All subjects)

Staff will administer a questionnaire to all subjects who perform fingerstick self-testing after the meter testing is completed.

The questionnaire will include statements for which a numerical score or rating will be provided by subjects (1=strongly disagree, 2=disagree, 3=neutral, 4=agree, 5=strongly agree). These numerically scored statements will be tabulated into frequency distributions. The following statements will be subject to the pass/fail criteria listed in the study objectives section:

- I find it easy to do a fingerstick blood test with this meter.
- The meter display is easy to see and read.
- It was easy to understand my test results.
- The instructions (User Guide and Quick Reference Guide) were easy to understand.
- The instructions clearly explain how to run a test.
- The instructions clearly explain what to do if an error message is displayed by the meter. *Note: an error message will be demonstrated by the study staff if the subject does not experience an error message during his/her testing.*

Per ISO 15197:2013, Section 8.8.2, the questionnaire will also contain a section whereby the subject can provide unrestricted comments on their experience about using the BGMS. This

questionnaire will be administered by the staff who will record the subject's responses. The subject will be given an example questionnaire to assist with providing the responses.

5.12.2 Questionnaire 2: BGMS Features. (Only subjects with diabetes)

After all testing and the first questionnaire have been completed, the study staff will demonstrate to only the subjects with diabetes several features of the BGMS that would not necessarily be experienced during the brief accuracy testing. This will ensure that the subjects are able to understand the features, and answer questions in the questionnaire.

There are no acceptance criteria for this questionnaire. This questionnaire may be 1) administered by the staff who will record the subject's responses or 2) completed by the subjects and verified by the study staff, as per site procedures. In the first scenario, the subject will be given an example questionnaire to assist with providing the responses.

5.13 Device Problem Reporting

Any functional problems with the T-Plus BGMS will be documented by the study staff and reported timely to Ascensia. The study staff should be specific about describing the problem and the sequence of events that led to it. All information will be documented on the Problem Reporter Form, including the meter type, serial number and test strip lot. Malfunctioning BGMs will be replaced and this will be documented for study tracking. If appropriate, such meters will be disinfected and shipped back to Ascensia for evaluation.

5.14 Temperature and Humidity Monitoring

The study staff will measure the temperature and humidity of the meter and YSI testing area(s) twice a day (AM and PM) using an audited thermometer/hygrometer supplied by Ascensia, and record the results on the appropriate form.

5.15 Miscellaneous

Ascensia representatives may observe subject visits as part of study staff training, study monitoring or for troubleshooting problems with the investigational devices. This will be done under supervision of the investigator.

Ascensia representatives may assist with disinfection of the meters, and perform centrifugation of blood samples and measurement of hematocrit.

Ascensia representatives will not train or interact in any way with the subjects. The presence of Ascensia representatives will be noted in the ICF.

Subjects will receive nominal compensation for their time and inconvenience.

6.0 Risk / Benefit Assessment

Risks associated with this study include those associated with obtaining blood from finger, palm and venipuncture.

The following risks are anticipated and will not be reported as Adverse Events (AE). (See section 7.0 for further details.)

- 1) Bleeding: Mild bleeding similar to being stuck with a pin
- 2) Swelling (Edema): A mild swelling similar to a mosquito bite
- 3) Bruising: Less than one inch across (fingerstick) or less than 2 inches across (venipuncture)
- 4) Redness (Erythema): Mild reddening or darkening of the skin in the immediate area around the puncture site
- 5) Soreness: Mild discomfort at the puncture site resolving (going away) within one to two days (fingerstick or palm) or within hours (venipuncture)

The following risks are unlikely, but possible, and will be reported as anticipated Adverse Events:

- 1) Bleeding: Continued bleeding requiring changing a bandage
- 2) Bruising: A worsening bruise that is firm to the touch
- 3) Redness (Erythema): Bright redness or skin darkening spreading across the area (fingerstick or palm) or across the arm (venipuncture)
- 4) Soreness: Worsening pain and/or pain that interferes with activity
- 5) Infection: Bright redness or skin darkening spreading across the area with warmth and/or swelling, and/or red streaking
- 6) Nerve injury: Numbness or shooting pain in the forearm
- 7) Numbness in the area of the puncture wound
- 8) Dizziness
- 9) Fainting

Subjects should be instructed to report such events to the investigator or designee.

Benefits

A benefit associated with the study is the sense of well-being gained by contributing to the development of improved or new blood glucose monitoring systems, which may be beneficial to people with diabetes or other associated diseases or conditions.

7.0 Adverse Event Management and Medical Device Reporting

The procedures to be performed under this protocol are considered to be low risk.

7.1 Description and Classification

7.1.1. An AE during a clinical evaluation is “any untoward medical occurrence, unintended disease or injury, or untoward clinical signs (including abnormal laboratory findings) in subjects, users or other persons, whether or not related to the investigational medical device.” It is not dependent on whether the event is considered to be related to the investigational product or the study. An AE includes events not seen at the beginning of the study, or worsened if present at the beginning. Adverse events can be classified as presented in Table 7.1.

7.1.2. The next classification to consider is whether or not the AE is Anticipated or Unanticipated. In order for an AE to be considered ‘anticipated’ it must be listed in the protocol and ICF prior to any occurrence.

7.1.3. For studies on products that have not yet been cleared for market, it is important that all AEs be documented and included in the study file.

7.1.4. An unanticipated adverse device effect (UADE) is: Any serious adverse effect on health or safety or any life-threatening problem or death caused by, or associated with a device, if that effect, problem or death was not previously identified in nature, severity or degree of incidence in the investigational plan or application (including a supplementary plan or application), or any other unanticipated serious problem associated with a device that relates to the rights, safety or welfare of subjects [21CFR812.3(s)].

7.1.5. All AEs observed by the Investigator or reported by the subject will be documented on the AE form (including all symptoms) and included in the study file.

7.2 Events related to hypoglycemia and hyperglycemia

Hypoglycemia and hyperglycemia can be a common occurrence with subjects who have diabetes. If it is found that a subject has a hypoglycemic event, as determined by the Principal Investigator (PI) during a study visit, the subject will be treated by the site staff accordingly. Appendices D and E note each site’s treatment plan.

Classification of the hypoglycemic or hyperglycemic event is at the discretion of the PI or designee. If the hypoglycemic or hyperglycemic event is considered by the PI as an AE, it will be considered to be an anticipated AE and will be recorded on the AE Form.

Subjects who are hypo- or hyperglycemic may continue with fingerstick testing if they so choose, and if the PI determines that it is safe. The PI will define what is considered to be a hypoglycemic or hyperglycemic state.

Table 7.1: Classification of Adverse Event

Serious*	Non-Serious

An adverse event that leads to:
 
 a) death; b) a serious deterioration in health of the subject that, 
 1) resulted in a life-threatening illness or injury, 2) resulted in a permanent impairment of a body structure or a body function, 3) required in-patient hospitalization or prolongation of existing hospitalization, 4) resulted in medical or surgical intervention to prevent permanent impairment to body structure or a body function; c) fetal distress or a congenital abnormality or birth defect. 
May be anticipated or unanticipated.
	
All adverse events not reported as serious. At each visit, all adverse events observed by the investigator/designate or reported by subject must be evaluated and recorded on an adverse event form.
 
A non-serious adverse event is further classified with respect to severity and relationship to the trial product. A non-serious adverse event may be anticipated or unanticipated.
 
Further classification with regard to severity
 
 • Mild: Transient symptoms, easily tolerated, no interference with subjects daily activities. • Moderate: Marked symptoms, moderate interference with subjects daily activities, and tolerable. • Severe: Considerable interference with subject's daily activities, not tolerable.

Relationship to trial product:

- Definitely Related: Causal relationship has been established and documented
- Probably Related: Good reasons and sufficient documentation to assume causal relationship have been established
- Possibly Related: Causal relationship is likely and cannot be excluded
- Probably Not Related: Good reasons and sufficient documentation not established to assume causal relationship
- Not Related: The event is most likely related to an etiology other than the trial treatment

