7.3 Procedure for Reporting an Adverse Event

Adverse events will be documented during this study by completing the AE Form. The Investigator or designee will sign and date an AE Form for each AE experienced by any subject. During the visit, AEs will be evaluated by a member of the study staff. The nature of each event and date of onset, outcome, course, maximum intensity and action taken with respect to treatment should be established. Details of any corrective treatment should be recorded on the AE Form. Investigators should follow-up on the status of subjects experiencing an ongoing AE until the event has been resolved, or until the condition has stabilized.

7.3.1. The Investigator or designee will notify the Study Manager or Monitor within 24 hours of any Serious Adverse Event that occurred during the study. The sponsor will promptly review all information relevant to the safety of the investigational device.

7.3.2. The investigator or designee must notify the sponsor and reviewing IRB by phone or fax of Unanticipated Serious Device-Related Adverse Events within 24 hours of learning of the event, followed by a written a report within 10 working days after learning of the event.

7.3.3. Upon receipt of a report of an UADE by the Ascensia Study Manager or Monitor, the report will be immediately forwarded to:

7.3.4. The sponsor (Ascensia) must report UADEs to the FDA, all participating investigators, and reviewing IRBs within 10 working days after the sponsor first receives notice of the event.

7.3.5. Regardless of the above definitions, any additional adverse experience that the investigator considers serious, and/or of concern in relationship to the study must be documented and reported to the Study Manager or Monitor within 24 hours.

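### The adverse-event relatedness scale sets *Possibly Related* at a likely link, so its categories overlap and a conceivable but not likely device event is recorded as *Probably Not Related*

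*Combined protocol and SAP*

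**What the plan says.** The scale follows Table 7.1 in section 7.2 of the protocol, under the heading "Relationship to trial product". Its top grade, *Definitely Related*, needs an established and documented causal link. The second, *Probably Related*, needs sound grounds and enough documentation to assume one. The middle grade is worded as "Possibly Related: Causal relationship is likely and cannot be excluded". The fourth, *Probably Not Related*, is for events where the grounds and documentation asked for in the second grade are lacking. The lowest grade names a different object from the one in the heading: "Not Related: The event is most likely related to an etiology other than the trial treatment".

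The sentence that puts the scale to use stands in the Non-Serious column of Table 7.1: "A non-serious adverse event is further classified with respect to severity and relationship to the trial product". The Serious column lists seriousness criteria and says such an event may be anticipated or unanticipated; it does not mention relationship.

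Section 6.0 says where the study's risks lie: "Risks associated with this study include those associated with obtaining blood from finger, palm and venipuncture". It then lists nine more marked reactions that are to be reported as anticipated adverse events.

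**The concern.** A causality scale should be ordered, and each event should have one place in it. The middle grade normally takes the uncertain events, where a link can be imagined and not ruled out but is not shown to be likely. Here the middle grade asks for a likely link, so those events drop to a grade whose label says the product was probably not the cause. Two graders who follow the text can also give the same event grades on opposite sides of the line between related and not related.

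Two further points add doubt about what is being graded. The heading speaks of the trial product and the last category of the trial treatment. The injuries the protocol expects come mainly from blood sampling, and the scale has no category for that.

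At stake is whether the recorded grades mean what their labels say when the sponsor, an IRB or a regulator reads them.

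**Working it through.** The protocol gives no figure for this point, so the check sets the definitions side by side and runs test events through them.

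**What each category requires**

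- *Definitely Related*: link established and documented.
- *Probably Related*: good reasons and sufficient documentation.
- *Possibly Related*: link likely, and not excludable. No documentation is required.
- *Probably Not Related*: good reasons and sufficient documentation are lacking. Nothing is said about how likely the link is.
- *Not Related*: another cause is most likely.

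**Event A: link conceivable but not likely, little documentation, no other cause more likely.** It fails the first three categories, the third because the link is not likely. It fails *Not Related* because no other cause is most likely. Only *Probably Not Related* remains.

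**Event B: link likely, little documentation.** It meets *Possibly Related*. It also meets *Probably Not Related*, because good reasons and documentation have not been established. Both grades follow from the text.

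**Event C: link likely, with good reasons and documentation.** It meets *Probably Related* and also *Possibly Related*, which sets no upper limit on evidence.

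A rule to take the highest category met would settle B and C. Sections 7.1 to 7.3 state no such rule, and it would not help A.

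**Event D: nerve injury after venipuncture.** Section 1.0 describes the investigational system as a meter plus test strips. If the trial product means that system, the injury falls under the lower grades. If the trial treatment is read to include study procedures, the answer can differ. Neither term is defined, so the grade depends on which line the grader reads. Section 7.1.1 itself mentions relation to the product and relation to the study as separate things, but the printed scale grades only one object.

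**Event class.** The only applying sentence names non-serious events. The scale itself is printed after the table under a heading with no such limit. The text was read from a PDF, and the asterisk on the Serious heading has no note in the text available. The restriction is therefore the literal reading, not a certain one.

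**Where a grade would be used.**

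- 7.1.5 puts every adverse event on the form.
- 7.3.1 sends every serious event to the sponsor within 24 hours.
- 7.3.2 requires notice to the sponsor and IRB of "Unanticipated Serious Device-Related Adverse Events within 24 hours of learning of the event" but does not cite Table 7.1.
- 7.1.4 defines the unanticipated device effect by whether it was caused by or associated with a device.
- The SAP contains no adverse-event analysis.

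None of these steps takes the five-level grade as its input.

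**The case against.** The best defence is that the two upper-middle grades still differ: *Probably Related* needs good reasons and documentation, and *Possibly Related* does not. That stands, so it would be wrong to say the two are the same grade. It does not help Event A, which fails both, or Event B, which meets two grades at once. The downgrading of A is an inference from the definitions; the protocol does not announce it.

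Several stronger readings are tempting, and the documents do not support them.

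- **Lancing and venipuncture injuries have no attribution at all.** Section 6.0 makes them reportable as anticipated events, several tied to the puncture site. Section 7.3 asks for nature, onset, course and outcome, and 7.4 gives a causal reporting route for the Microlet NEXT lancing device. Section 7.3.5 catches anything of concern in relation to the study. What is missing is a graded procedure category, most clearly for the Tenderlett lancing and venipuncture. The adverse-event form is not among the documents, so it may already hold such a field.
- **Relatedness figures will be biased.** No table or analysis by relatedness is planned, so only individual recorded grades can be wrong.
- **The 24-hour IRB notice rests on a grade nobody assigns.** Section 7.3.2 does not use the scale, and 7.1.4 sets its own, broader test of device association.
- **None of the expected adverse events can be classified correctly.** The nine items in 6.0 are not the full set, since 7.2 also treats hypoglycemia and hyperglycemia as anticipated events when judged adverse. The ceiling of 15 puncture attempts for a subject with diabetes (3 attempts at each of 5 sampling steps) counts attempts and says nothing about misgrading.

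**Conclusion.** The wording fault is real. As written, *Possibly Related* excludes the conceivable but not likely event, and *Probably Not Related* overlaps with it for likely but undocumented events. The inconsistent object and the missing statement on event class are secondary faults of the same scale; the second carries the layout caveat given above.

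The size is small. No event is lost, no notice to the sponsor waits on the grade, and no accuracy result, sample size or power statement changes. The effect is limited to the recorded relatedness grades. It cannot be put as a number, because the documents give no expected count of adverse events.

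The conclusion assumes that graders apply the printed definitions literally, and that no instruction outside these documents, such as on the form itself, overrides them. It ranks as a minor correction, worth making because it costs almost nothing.

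**What to change.** 1. In *Possibly Related*, replace the requirement that the link is likely and cannot be excluded with one that it is conceivable and cannot be excluded. This one-word change gives Event A its proper place.
2. Use one object throughout the scale, in the heading and in *Not Related*, and define it.
3. State with Table 7.1 that relationship is graded for serious and non-serious events alike.
4. Optionally, add a field to the adverse-event form for relationship to study procedures (lancing, Tenderlett, venipuncture), unless the form already has one.

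The cost is a few words in section 7.2 and at most one extra field. The downside is that slightly more events will be graded as related. No objective, procedure or analysis changes.

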7.3 Procedure for Reporting an Adverse Event

Adverse events will be documented during this study by completing the AE Form. The Investigator or designee will sign and date an AE Form for each AE experienced by any subject. During the visit, AEs will be evaluated by a member of the study staff. The nature of each event and date of onset, outcome, course, maximum intensity and action taken with respect to treatment should be established. Details of any corrective treatment should be recorded on the AE Form. Investigators should follow-up on the status of subjects experiencing an ongoing AE until the event has been resolved, or until the condition has stabilized.

7.3.1. The Investigator or designee will notify the Study Manager or Monitor within 24 hours of any Serious Adverse Event that occurred during the study. The sponsor will promptly review all information relevant to the safety of the investigational device.

7.3.2. The investigator or designee must notify the sponsor and reviewing IRB by phone or fax of Unanticipated Serious Device-Related Adverse Events within 24 hours of learning of the event, followed by a written a report within 10 working days after learning of the event.

7.3.3. Upon receipt of a report of an UADE by the Ascensia Study Manager or Monitor, the report will be immediately forwarded to:

7.3.4. The sponsor (Ascensia) must report UADEs to the FDA, all participating investigators, and reviewing IRBs within 10 working days after the sponsor first receives notice of the event.

7.3.5. Regardless of the above definitions, any additional adverse experience that the investigator considers serious, and/or of concern in relationship to the study must be documented and reported to the Study Manager or Monitor within 24 hours.

7.4 Medical Device Reporting

The Microlet NEXT lancing device system is an Ascensia marketed product in the US. If an AE occurs that is directly caused by the marketed product, the AE should be reported immediately, but in any case within 24 hours, to the Customer Service Department at [name]. Also contact the Ascensia representative listed in Section 12.0.

8.0 Study Termination and Subject Withdrawal Criteria

8.1 Criteria to Withdraw / Discontinue a Subject from Study

Subjects who experience an AE will be withdrawn from the study. Subjects may be withdrawn from the study at their own request for any reason, or at the discretion of the PI (or designee) for one of the following reasons:

- 1) Illness of a subject
- 2) Subject non-compliance with protocol requirements
- 3) Other, at the discretion of the investigator

In such cases, the subject will be withdrawn from further study participation. Any evaluable data collected from withdrawn subjects will be analyzed and results will be retained for safety assessments. If available, data will be retained in analyses related to the objectives of the study unless there is a valid reason to believe that the data may be biased, incorrect, or confounded.

